10.21.3 Visual Analogue Scale

Pain will be assessed by VAS (0 – 100 mm). The VAS scale ranges from 0 mm meaning “no overall pain” and 100 mm meaning “worst overall pain imaginable.” Subjects will be asked to report pain intensity “in the last 72 hours” by marking a line perpendicular to the VAS line at the point that represents their pain intensity. Site personnel will determine the score by measuring the distance (mm) on the 100-mm line between the left, “no pain” anchor and the subject’s mark, measuring the total distance of the line (to ensure that it is 100 mm), and dividing the distance from the “no pain” mark to the subject’s mark by the total distance of the line. The scored VAS ranges from 0 – 100.

**Evaluation of Long-term Patient Experience with a
Medtronic Closed-Loop SCS System (Closed-Loop SCS study)**

Clinical Investigation Plan

06JAN2023

Version 4.0

Page 50 of 117

Medtronic

[REDACTED]

[REDACTED]

[REDACTED]

[REDACTED]

[REDACTED]

[REDACTED]

[REDACTED]

[REDACTED]

[REDACTED]

[REDACTED]

[REDACTED]

[REDACTED]

[REDACTED]

[REDACTED]

[REDACTED]

[REDACTED]

10.22 Assessment of Safety

To characterize all device-related, therapy-related, and procedure-related adverse events and device deficiencies. Adverse events and device deficiencies will be summarized using summary tables displaying the frequency and percentages, by study phase, and in total. Adverse events will be summarized by seriousness as well.

See Section 12 for further information on the collection of AEs and safety information.

10.23 Recording Data

Data entered must be traceable to source documents. Source documentation is defined as the first time data appear, and may include original documents, data, and records (e.g., hospital records, clinical and office charts, procedure reports, laboratory notes, memoranda, subjects' diaries or evaluation checklists, pharmacy dispensing records, recorded data from automated instruments, copies or transcriptions certified after verification as being accurate copies, microfiches, photographic negatives,

[REDACTED]

[REDACTED]

microfilm or magnetic media, X-rays, subject files, device data and records kept at the pharmacy, at the laboratories and at medico-technical departments involved in the study).

Interrogation files will be collected and stored at the site. Pseudonymized copies of the interrogation files submitted to Medtronic should be sent via secure and compliant electronic file transfer services and/or secure mail.

Fluoroscopy or x-ray images shall be collected and stored on a CD/DVD or USB flash drive at the site. Pseudonymized copies of those images submitted to Medtronic shall be sent via secure and compliant electronic file transfer services and/or secure mail.

In general, eCRFs (or paper copies) may not serve as source documents. An exception may be the completion of questionnaires and clinical scales. Source documentation for data elements not routinely captured in medical records may vary from study site to study site; the study site may use source document worksheets if identified as source documents.

The Investigator must ensure the availability of source documents from which the information on the eCRFs was derived. The type and location of source documents should be documented. Where printouts of electronic medical records, are provided as source documents, or where copies of source documents are retained as source documents, those should be certified. Certification must contain (1) the signature of the individual making the copy, (2) the date the copy was made.

The source documents must be made available for monitoring or auditing by Medtronic's representative or representatives of the competent authorities and other applicable regulatory agencies.

The CRF may be considered source for the following data collection elements:

- Enrollment Notification
 - Study site assigned subject reference
- Baseline
 - Administrative information
- AE eCRF
 - Date study site became aware of event
 - Relatedness of adverse event
- Device Deficiency eCRF
 - Date study site became aware of event
- Subject Death
 - Date study site became aware of death
 - Relatedness of death
 - System explant information
- Deviations
 - Reason for deviation

10.24 Deviation Handling

A study deviation is defined as an event within a study that did not occur according to the CIP or the CTA.

Prior approval by Medtronic is expected in situations where the investigator anticipates, contemplates, or makes a conscious decision to deviate. Prior approval is not required when a deviation is necessary to protect the safety, rights or well-being of a subject in an emergency or in unforeseen situations beyond the investigator's control (e.g. subject failure to attend scheduled visits, inadvertent loss of data due to computer malfunction, inability to perform required procedures due to subject illness).

For medically justifiable conditions which preempt a subject's ability to complete a study-required procedure, it may be permitted to report only one deviation which will apply to all visits going forward. This may also apply for other unforeseen situations (e.g. the subject permanently refuses to complete a study required procedure and the data will not contribute to the primary end point analysis). However, prior approval from Medtronic is required for such situations.

All study deviations must be reported on the CRF regardless of whether medically justifiable, pre-approved by Medtronic, an inadvertent occurrence, or taken to protect the subject in an emergency. Multiple deviations of the same type at the same visit may be reported on one case report form.

In the event the deviation involves a failure to obtain a subject's consent, or is made to protect the life or physical well-being of a subject in an emergency, the deviation must be reported to the EC as well as Medtronic within five (5) working days. Reporting of all other study deviations should comply with EC policies and/or local laws and must be reported to Medtronic as soon as possible upon the study site becoming aware of the deviation. Reporting of deviations must comply with EC policies, local laws, and/or Regulatory Authority requirements. Refer to Investigator Reports, Table 8 for deviation reporting requirements and timeframes for reporting to Medtronic and/or Regulatory Authority.

Medtronic is responsible for analyzing deviations, assessing their significance, and identifying any additional corrective and/or preventive actions (e.g. amend the CIP, conduct additional training, terminate the investigation). Repetitive or serious investigator compliance issues may result in initiation of a corrective action plan with the investigator and study site, and in some cases, may necessitate suspending enrollment until the problem is resolved or ultimately terminating the investigator's participation in the study. Medtronic will provide study site-specific reports to investigators summarizing information on deviations that occurred at the investigational study site on a periodic basis.

Examples of study deviations include but are not limited to:

- Failure to obtain proper IC
- Failure to collect required study data
- Inclusion/exclusion criteria not met
- Missing required device interrogation files
- Visits out of window

10.25 Subject Exit, Withdrawal or Discontinuation

10.25.1 Study Exit

A study exit eCRF is required for all subjects. Prior to exiting a subject from the study, it is recommended to follow the subject until all ongoing system and/or procedure related AEs are resolved or unresolved

with no further actions planned, or until official study closure, whichever occurs first. Following exit, subjects will continue to receive standard medical care as they would have received a commercially available SCS device and be followed per Investigator discretion. Upon exiting from the study, no further study data will be collected or study visits will occur for the subject. All data available through the time of the subject's exit will be used for analysis.

Subjects are urged to remain in the study as long as possible but may be exited from the study for any of the following situations:

- Study completed
- Subject lost to follow-up
- Subject death
- Subject did not meet inclusion/exclusion criteria
- Subject was not implanted with the study device
- Subject did not provide informed consent
- Subject chooses to withdraw (e.g., consent withdrawal, relocation to another geographic location)
- Investigator deems withdrawal necessary (e.g., medically justified, inclusion/exclusion criteria not met, failure of subject to maintain adequate study compliance)

Complete an Unscheduled Visit if the subject exits early, between visits and prior to the last study visit:

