14.5.1.4 Determination of Subjects/Data for Analysis

Information from low-back and/or leg pain subjects who provide data at baseline and the 3-Month Visit (low-back and/or leg pain subjects from the CCS) will be used for this objective.

As a sensitivity analysis, if there is greater than 5% of subjects with missing values, any subjects who were device-implanted (FAS) but are missing their VAS scores at the 3-Month Visit will be imputed using Multiple Imputation (MI). Prior to the use of MI, the distributions of the continuous variables will be assessed for normality and transformation may be considered if they are not normally distributed.

Following imputation, the objective will be evaluated using MI analysis method.

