7.1.3 Analysis Sets

- The **All Consented Set** (ACS) will include all subjects who signed the study specific ICF and enrolled in the study.
- The **Full Analysis Set** (FAS) will include all device-implanted subjects.
- The **Primary Analysis Set** (PAS) will follow the intent-to-treat (ITT) principle to include randomized low-back and leg pain subjects who will be used for the primary objective, i.e., the first 28 randomized low-back and leg pain subjects.
- The **Complete Case Set** (CCS) will include all device-implanted subjects who have data available at baseline and follow-up. This set is defined for each outcome measure at each follow-up visit. [REDACTED]

[REDACTED]

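### Section 10.25.1 lets implanted subjects be exited for unmet eligibility criteria or poor compliance, which can remove them from the 3-Month responder analysis and end their later follow-up

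*Protocol*

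**What the plan says.** Protocol Section 10.25.1 lists the reasons for which a subject may be exited. Unmet eligibility appears twice: once alone ("Subject did not meet inclusion/exclusion criteria") and once inside the investigator-decision reason ("Investigator deems withdrawal necessary (e.g., medically justified, inclusion/exclusion criteria not met, failure of subject to maintain adequate study compliance"). Neither entry is tied to a stage of the study. Adequate compliance is not defined, and the section states no sponsor review of the exit.

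On the consequence, the section says: "Upon exiting from the study, no further study data will be collected or study visits will occur for the subject". Earlier data are kept: "All data available through the time of the subject's exit will be used for analysis". For early exits it adds: "Complete an Unscheduled Visit if the subject exits early, between visits and prior to the last study visit". The visible list of data for an Unscheduled Visit (Section 10.18) does not include VAS. In the visible schedule of events, VAS is collected only at baseline and at the 3- to 24-Month visits.

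Secondary objective 1 is the percentage of implanted low-back/leg subjects with at least 50% improvement in overall VAS at 3 months. Its main analysis uses "Information from low-back and/or leg pain subjects who provide data at baseline and the 3-Month Visit" (Protocol 14.5.1.4; SAP 7.9.2.1.4 agrees). Protocol 14.5.2.4 takes the same approach for back and leg pain. In these sections, multiple imputation over the Full Analysis Set (FAS) is a sensitivity analysis, used if more than 5% are missing. The FAS "will include all device-implanted subjects" (SAP 7.1.3). SAP 7.4 differs: it names the FAS for all secondary objectives, with imputation above 5% missing.

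**The concern.** Exit for ineligibility is ordinary before implant, and Sections 10.7 and 10.8 already provide for it. After implant the same exit reasons create missing data that can be related to outcome.

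Section 10.17 has sites record a 0-10 pain score by telephone each week from activation to the 3-Month Visit, except in weeks with a study visit. The site therefore knows how a subject is doing before the 3-Month VAS is taken. Psychiatric comorbidity, other confounding disease and drug-related behaviour are left to the investigator's determination, and compliance has no stated threshold. A subject who is doing badly could be judged ineligible or non-compliant more readily than one who is doing well.

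Two things are at stake. The first is the 3-Month responder rate, which rises if non-responders leave the denominator. The second is the 6- to 24-Month record: safety is characterised only until study exit (Protocol 14.7, SAP 7.10), in a device that the SAP introduction describes as not previously studied in humans in its fully implantable form.

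**Working it through.** **Plan figures.** The documents give no visible rate for these exits, so there is no plan figure on this point to reproduce. The primary sample size is a separate matter and does reproduce: with n = 28, p0 = 50%, p1 = 80% and one-sided alpha 0.025, the exact rule is at least 20 successes, with type I error 0.0178 and power 0.910, against the stated figure of more than 90%.

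**Which exits matter for which result.**
- Before implant: the subject is in neither the FAS nor the Complete Case Set (CCS), so the responder rate is unaffected.
- From implant to the 3-Month Visit (day 90 ± 15 from activation): no 3-Month VAS, so the subject is not in the CCS.
- After the 3-Month Visit: the 3-Month result is kept, but later efficacy and safety data are lost.

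**Illustration.** Assumed inputs, not from the documents: 48 implanted low-back/leg subjects, 34 responders, and k non-responders exited before 3 months with no other missing data. Complete-case rate = 34/(48 − k).

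| k | Rate | Change from 70.8% |
|---|---|---|
| 0 | 34/48 = 70.8% | – |
| 1 | 34/47 = 72.3% | +1.5 points |
| 3 | 34/45 = 75.6% | +4.7 points |
| 5 | 34/43 = 79.1% | +8.2 points |

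**Same calculation at the protocol's maximum of 57 low-back/leg implants**, with assumed true responder counts R. Rate = R/(57 − k).

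| R | All implanted | k = 2 | k = 5 |
|---|---|---|---|
| 34 | 59.6% | 34/55 = 61.8% | 34/52 = 65.4% |
| 40 | 70.2% | 40/55 = 72.7% | 40/52 = 76.9% |
| 46 | 80.7% | 46/55 = 83.6% | 46/52 = 88.5% |

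Two exits add about 2 to 3 points; five add about 6 to 8.

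**Does imputation repair this?**
- Trigger: 0.05 × 57 = 2.85 subjects. If nothing else is missing, one or two exits (1.8%, 3.5%) trigger no imputation. Other attrition counts towards the trigger too. If only 45 of 57 reached 3 months, 12/57 = 21.1% would be missing and imputation would run.
- Content: the visible text does not show the imputation model. If its predictors do not separate exited subjects from those who stayed, it fills in at about the complete-case rate. In the first table with k = 3, the expected result is (34 + 3 × 34/45)/48 = 36.27/48 = 75.6%, the same as the complete-case figure and not 70.8%. A model with informative predictors could do better, but the actual 3-Month score has still not been collected.

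**The case against.** Several points on the other side stand.

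- Section 10.25.1 urges subjects to stay as long as possible. Exit is permitted, not required, and the list covers everyone from consent onward (up to 140 enrolled), so the eligibility reasons have an ordinary pre-implant use.
- The secondary objectives have no hypothesis test. The consequence is bias in a descriptive estimate, not inflated type I error.
- The shift is small against the precision: the exact 95% interval for 34/48 is 55.9% to 83.0%, which contains 79.1%. That limits the scale but does not remove the bias.
- Exits are not hidden. An exit form is required for every subject, and attrition and deviations are summarised.
- A non-compliant subject who misses the 3-Month VAS is outside the CCS whether exited or not, so a change to 10.25.1 closes only part of the gap.

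Four stronger readings are tempting, and the documents do not support them.

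1. A reader might infer that Section 10.24 requires an ineligible subject to be kept, and so contradicts 10.25.1. It only gives "Inclusion/exclusion criteria not met" as an example of a deviation. Reporting a deviation and then exiting the subject are compatible.
2. A reader might blame the lack of site blinding. The blind in Section 10.15.3 concerns the On/Off order at in-clinic testing. The 3-Month responder rate is a single-group change from baseline with no assignment to unblind. The relevant knowledge is the pain status from the weekly calls.
3. A reader might treat imputation over the FAS as settled to be a sensitivity analysis only. SAP 7.4 says otherwise, and the conflict is open.
4. A reader might extend the point to the primary test. That endpoint is measured at about 30 days in randomised subjects under the ITT principle, and is largely outside it.

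**Conclusion.** The point holds as a weakness in the exit rule. Section 10.25.1 permits an implanted subject to be removed on a judgement that can be related to outcome, and data collection stops at exit. The main responder analysis then omits that subject, although the objective counts all implanted subjects. Under either SAP reading of the analysis set, the missing score is not recovered.

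The size is modest: about 1.5 points for one non-responder exit and up to about 8 for five. These figures assume 48 or 57 implanted, true responder rates of about 60% to 81%, and that every exit is a non-responder leaving before the 3-Month Visit. The documents permit such exits but do not show that any has occurred or is intended. The version history reports higher attrition than expected, but its visible text gives no cause. Some analysis text is redacted, so a further safeguard there cannot be excluded. The change is worth making because it is cheap and also protects the 6- to 24-Month follow-up.

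**What to change.** In Protocol Section 10.25.1:

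- Limit both eligibility-failure reasons to subjects not yet implanted.
- Remove poor compliance as a reason to end study follow-up of an implanted subject.
- State that an implanted subject found not to meet a criterion, or who complies poorly, is reported as a deviation under Section 10.24 and continues scheduled VAS and safety visits. That subject stays in the FAS, and in the Primary Analysis Set and CCS as the data allow.
- Leave the subject's own withdrawal and medically justified withdrawal unchanged. The amendment concerns study follow-up only, not treatment.

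In the SAP, reconcile Section 7.4 with 7.9.2.1.4 (and with Protocol 14.5.1.4 and 14.5.2.4) on whether the main secondary analysis uses the CCS or the FAS with imputation. It would help to report exits after implant by reason, and to add a responder rate over all implanted low-back/leg subjects with missing counted as non-response. Section 12.3, which asks for continued follow-up of ongoing device- or procedure-related events after early exit, should be reconciled with the 10.25.1 statement that data collection stops.

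The cost is a wording amendment. The visits are already scheduled. Some ineligible or poorly compliant subjects will remain in the data, and the responder rate may be slightly less favourable.

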10.17 Phone Calls

Subjects will be called every week starting after Device Activation through the 3-Month Visit and monthly thereafter with an exception for the weeks or months when the subject has a study required visit. If the subject reports being Unsatisfied with the therapy, as determined by the phone call, the subject may be brought in for an Unscheduled visit for further therapy optimization.

The following information is required to be collected during the phone calls:

- Pain Relief Status
 - Pain score on the 11-point Numeric Rating Scale (NRS) of 0 - 10; 0 being no pain and 10 being worst imaginable pain.
- Pain medications changes
- AEs/device deficiencies

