10.18 Unscheduled Visits

Unscheduled visits may occur if programming changes are required to correct programming errors, to reprogram for pain optimization, or for an AE. Whenever feasible, subjects should have their devices interrogated.

The following information is required to be collected during unscheduled visits:

- Reason for visit
- If applicable, collect data files via the clinician programmer tablet and securely send to Medtronic
- Fluoroscopy/x-ray, if necessary
- Pain medications changes
- AEs/device deficiencies

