10.20 System Modification

System modifications (e.g. lead or device revision, replacement, or explant) may occur in the study due to ineffective or loss of therapy, AEs, device deficiencies, or subject concerns that are not correctable by programming. In the event of a system modification, the visit schedule for the subject will remain unchanged. If the SCS device requires replacement, contact a member of the Medtronic study team as the decision to allow re-implant will be handled on a case-by-case basis. If the system is explanted, the explanted system will be returned to Medtronic. All explanted products should be returned to Medtronic for analysis when permissible by local laws and regulations. See Sections 7.10 and 7.11 for final product disposition details.

The following information is required to be collected during system modification visits:

- Changes to the implanted system
- Collect data files via the clinician programmer tablet and securely send to Medtronic
- Fluoroscopy/x-ray, if necessary
- Pain medications
- AEs/device deficiencies

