14.7 Safety Assessment

To characterize all device-related, therapy-related, and procedure-related adverse events and device deficiencies from the start of the device trial until study exit. Adverse events and device deficiencies will be summarized using summary tables displaying the frequency and percentages of events as well as the number of subjects experiencing events, by study phase, and in total. Adverse events will be summarized by seriousness as well.

[REDACTED]

[REDACTED]

[REDACTED]

[REDACTED]

[REDACTED]	[REDACTED]	[REDACTED]	[REDACTED]	[REDACTED]
[REDACTED]	[REDACTED]	[REDACTED]	[REDACTED]	[REDACTED]
[REDACTED]	[REDACTED]	[REDACTED]	[REDACTED]	[REDACTED]
[REDACTED]	[REDACTED]	[REDACTED]	[REDACTED]	[REDACTED]
[REDACTED]	[REDACTED]	[REDACTED]	[REDACTED]	[REDACTED]
[REDACTED]	[REDACTED]	[REDACTED]	[REDACTED]	[REDACTED]
[REDACTED]	[REDACTED]	[REDACTED]	[REDACTED]	[REDACTED]
[REDACTED]	[REDACTED]	[REDACTED]	[REDACTED]	[REDACTED]
[REDACTED]	[REDACTED]	[REDACTED]	[REDACTED]	[REDACTED]
[REDACTED]	[REDACTED]	[REDACTED]	[REDACTED]	[REDACTED]

For the primary objective, a subset (28) of the total device implanted low-back and/or leg pain subjects are needed to evaluate the endpoint. For the secondary objectives, up to 45 implanted subjects with low-back and/or leg pain are desired to characterize the responder rates at the 3-Month Visit. Up to 9 implanted subjects with upper limb and/or neck pain are desired to characterize the population at the 3-Month Visit.

[REDACTED]

[REDACTED]

[REDACTED]

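### No VAS is listed at the early-exit visit, so an implanted subject who leaves before 3 months has no post-baseline VAS for the responder analyses

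*Protocol*

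**What the plan says.** CIP 10.25.1 sets the exit procedure: "Complete an Unscheduled Visit if the subject exits early, between visits and prior to the last study visit". It adds "Upon exiting from the study, no further study data will be collected", and also "All data available through the time of the subject's exit will be used for analysis".

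CIP 10.18 introduces its list with "The following information is required to be collected during unscheduled visits". The items are the reason for the visit, data files, imaging, pain-medication changes, and adverse events or device deficiencies. CIP 10.20 has a similar list, introduced by "The following information is required to be collected during system modification visits". VAS is in neither. In the schedule table of CIP section 10, the VAS row is readable. It is marked at Enrollment/Baseline and at the 3- to 24-Month Visits, and is blank under Unscheduled and System Modification.

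On the analysis side, CIP 14.5.1 and SAP 7.9.2.1 define the responder rate over implanted subjects. CIP 14.5.1.4 and 14.5.2.4 and SAP 7.9.2.1.4 compute it on the complete case set, which under SAP 7.1.3 "will include all device-implanted subjects who have data available at baseline and follow-up". If more than 5% of subjects have missing values, these sections add a sensitivity analysis that imputes the missing 3-month VAS in the full analysis set (FAS). SAP 7.4 instead assigns all secondary objectives to the FAS, with MI above 5% missing.

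**The concern.** No VAS is scheduled between baseline and 3 months. A subject who is implanted and then exits in that interval leaves a baseline VAS and nothing later on the scale that defines response. The exit visit is the last chance to obtain one, and its list does not ask for it. The promise to use all data up to exit then adds no VAS for this subject.

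If leaving is related to poor pain relief, a rate computed on those who stay is too high for the implanted population in the definition. The documents give no figure for how often this happens. CIP 10.20 does name ineffective or lost therapy as a reason for system modification, and CIP 14.9 itself lists missing data as a potential source of bias. At stake is how far the two descriptive responder rates can be read as rates among implanted subjects.

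**Working it through.** **Tracing one subject.** Take a low-back/leg subject who is implanted and activated, and who exits on day 60.

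1. VAS at baseline: yes (CIP 10.8).
2. VAS between baseline and exit: none marked in the schedule table.
3. VAS at exit: the visit is an Unscheduled Visit (10.25.1), and its list has no VAS (10.18).
4. VAS after exit: none, since data collection stops (10.25.1).
5. Other pain data: CIP 10.17 asks at phone calls for "Pain score on the 11-point Numeric Rating Scale (NRS) of 0 - 10". Calls are weekly from Device Activation to the 3-Month Visit, except in weeks with a required visit.
6. Main responder rate: excluded, because there is no 3-month VAS.
7. MI analysis: included if the 5% trigger is met, with no post-baseline VAS.

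**Inputs for the size.** The attrition table is blacked out, so there is no stated 3-month attrition figure to reproduce. The shortfall has to be inferred.

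- Low-back/leg subjects implanted, N: up to 57 (CIP section 6 and 10.8) or up to 50 (SAP section 5).
- Wanted at 3 months: 45. The sample-size text after CIP 14.7 says "up to 45 implanted subjects with low-back and/or leg pain are desired to characterize the responder rates at the 3-Month Visit", and SAP section 6 gives the same number.
- Responder rate among completers: assumed 80% for illustration, so x = 0.80 × 45 = 36.

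**Formulas.** Missing m = N − 45. Lowest rate among all implanted = x/N (no missing subject responds). Highest = (x + m)/N (all respond). The width is m/N whatever rate is assumed.

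| | CIP | SAP |
|---|---|---|
| m | 57 − 45 = 12 | 50 − 45 = 5 |
| m/N | 12/57 = 21.1% | 5/50 = 10.0% |
| Complete cases | 36/45 = 80.0% | 36/45 = 80.0% |
| Lowest | 36/57 = 63.2% | 36/50 = 72.0% |
| Highest | 48/57 = 84.2% | 41/50 = 82.0% |

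Exact 95% intervals are 65.4% to 90.4% for 36/45, 49.3% to 75.6% for 36/57, and 72.1% to 92.5% for 48/57. With the CIP numbers and an assumed 60% rate (27/45), the range is 27/57 = 47.4% to 39/57 = 68.4%, again 21 points wide.

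**Smaller shortfalls.** With 3 missing beside 45 completers, the range is 36/48 = 75.0% to 39/48 = 81.3%.

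**The 5% trigger**, taking the 57 low-back/leg subjects as the denominator: 3/57 = 5.3% starts the MI and 2/57 = 3.5% does not. Below the trigger, with 44/55 = 80.0% among completers, the range is only 44/57 = 77.2% to 46/57 = 80.7%.

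**The case against.** Several stronger readings are tempting, and the documents do not support them.

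- *A reader might infer that early leavers have no pain score at all after baseline.* CIP 10.17 collects an NRS at phone calls, and the synopsis records self-reported pain relief at trial lead explant. What is missing is a VAS. The NRS is only a partial substitute: 10.17 lists a single score on another scale, with no separate back and leg ratings. Calls are not needed in weeks with a required visit, so someone leaving during the optimization weeks may have few scores.
- *A reader might infer that leavers vanish from every analysis.* That is true of the complete-case rate only. Above 5% missing, MI brings them back as a sensitivity analysis, or in the main analysis if SAP 7.4 governs. The inferred shortfalls of 21% and 10% both exceed the trigger.
- *A reader might infer that the MI is bound to miss an outcome-related loss.* The imputation model is partly blacked out. Whether it uses the NRS or other auxiliary data cannot be seen.
- *A reader might infer that explant means no 3-month VAS.* CIP 10.20 keeps the visit schedule unchanged after a system modification. A subject who is explanted but stays is still due that VAS.
- *A reader might take all 12 of 57 to be leavers whom an exit VAS would inform.* Both figures are upper limits. The gap may also include missed visits, deaths and losses to follow-up.

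Two further objections deserve an answer. The sentence in 10.25.1 ends in a colon, so a list of exit assessments may be missing from the text as read. The schedule table is separate evidence, however, and its VAS row is blank under Unscheduled. It is also true that an exit VAS would not put anyone into the complete case set, which needs 3-month data. Its value lies in informing the imputation.

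**Conclusion.** The point holds in a limited form. On the readable text, no VAS is planned at the early-exit visit, so an implanted subject who exits before 3 months has no post-baseline VAS. The subject is outside the complete-case responder rates, and the MI has no post-baseline VAS to work from.

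Under the planned numbers and an assumed 80% completer rate, the rate among all implanted is uncertain by up to 21 points (CIP) or 10 points (SAP). These are outer bounds. They treat the whole inferred shortfall as unknown, ignore the NRS, and include subjects from whom no exit VAS could be obtained. With few leavers the effect is small.

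The study is a feasibility study, both secondary objectives are descriptive with no test, and the primary endpoint does not use VAS. The weight is minor to moderate, and the change is worth making because it is cheap. Counting leavers as responders or non-responders by an early exit VAS would be a new and debatable estimand, and is not needed.

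**What to change.** 1. In CIP 10.18, 10.25.1 and the schedule table, require the overall and pain-specific VAS at an Unscheduled Visit that serves as an early exit.
2. In CIP 10.20 and the schedule table, require the same at a System Modification visit that removes the system when the subject also exits.
3. In the SAP, name the exit VAS and the phone-call NRS already collected as auxiliary predictors in the MI sensitivity analysis for the 3-month VAS.
4. Reconcile SAP 7.4 (FAS) with SAP 7.9.2.1.4 (complete cases), so that it is clear which set carries the main responder rate.

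The cost is one paper form at a visit that already takes place, an eCRF field and an SAP edit. Subjects who are lost or refuse the exit visit stay missing, so the change narrows the gap without closing it.
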